14.0 Sample Size and Eligibility

14.1 Number of subjects that will be enrolled at UCSF and affiliated institutions:

120

14.2 Total number of subjects that will be enrolled at all sites (Help Text updated 9/13):

120

14.3 Estimated number of people that you will need to consent and screen here (but not necessarily enroll) to get the needed subjects:

218

14.4 Explain how and why the number of subjects was chosen (Help Text updated 9/13):

Although our primary analytic approach will be mixed effects linear regression models using a waitlist design, sample size estimates and power calculations are based on the simpler (and more conservative) situation of a repeated measures design with 1 pre and 2 post measures using effect size estimates from our pilot study, correlation between measures of 0.75 (based on our pilot data) and estimated alpha=0.03 (to account for multiple comparisons for our three co-primary outcomes). Sample size estimates at 80% power ranged from n=12/group to n=59/group depending on the effect size. Conversely, power estimates using a sample size of 60/group ranged from 81% to 100%. Power ranged from 71% to 100% for all outcomes even with 20% attrition. We estimate that we will need to contact and screen 218 potential study participants in order to enroll our target sample of 120 based on our pilot study response rate of 55%.

Sample Size and Power Estimates	Effect Size	Sample size, 80% Power	Power, N=60/ Group	Power, 20% Attrition
Co-Primary Outcomes				
Cognitive function (ADAS-cog)	0.76	12	1.00	1.00
Physical performance (SPPB)	0.34	59	0.81	0.71
Quality of life (QOL-AD)	0.83	10	1.00	1.00
Secondary Outcomes				
Caregiver burden (CBI)	0.49	29	0.97	0.92

14.5 * Eligible age range(s):

- 0-6 years
- 7-12 years
- 13-17 years
- 18+ years

14.6 Inclusion criteria:

We propose to enroll 120 dyads of individuals with dementia and their primary caregivers, with a goal of 20 dyads per intervention site. Veterans with dementia who are current clients at the site will be prioritized for enrollment. If we are unable to enroll our target sample of 20 Veterans with dementia at a given site, enrollment will be opened to non-Veterans with dementia at the site as well as Veterans and non-Veterans with dementia who are not currently clients at the site but are living in the community near the site and willing to attend for the study. Caregivers are not required to be Veterans, but their participation is necessary because they are providing care to the primary participants, many of whom will be Veterans.

Inclusion criteria, primary participant:

- diagnosis of memory loss or dementia
- mild to moderate severity (defined as Clinical Dementia Rating of 0.5, 1, or 2)
- English language fluency
- attendance or willingness to attend adult day health center at least 2 days/week on days that PLIE will be offered

Inclusion criteria, caregivers:

- Provide care for primary participant
- Able to answer study questionnaires related to participant's functional status, dementia-related behaviors, quality of life and their own feelings about caregiving
- English language fluency

14.7 Exclusion criteria:

Exclusion criteria, primary participant:

- Plans to change days of attendance during the study period so that participant would no longer be attending on at least 2 PLIE days/week
- Planning to leave the facility during the study period and not willing to come for PLIE classes at least 2 days/week
- Severe vision or hearing impairment (e.g., unable to see or hear well enough to follow instructions)
- Several physical impairment (e.g., paralysis or hemi-paralysis; wheel-chair or bed bound)
- Severe mental health condition (e.g., uncontrolled depression, PTSD, bipolar disorder)
- Limited life expectancy (e.g., enrolled in or eligible for hospice; metastatic cancer)
- Started dementia medication (cholinesterase inhibitor or memantine) in past 3 months
- Planning to change dementia medication during the study period
- Current participation in another research study
- Lack of legal supporting documentation for HIPAA (e.g., durable power of attorney, court ordered legal guardianship, advance health directives), If determined to lack capacity to consent.
- Lack of consent/assent to study procedures

Exclusion criteria, caregivers:

- Severe vision or hearing impairment (e.g., unable to see or hear well enough to follow instructions)
- Several physical impairment (e.g., paralysis or hemi-paralysis; wheel-chair or bed bound)
- Severe mental health condition (e.g., uncontrolled depression, PTSD, bipolar)
- Limited life expectancy (e.g., enrolled in or eligible for hospice; metastatic cancer)
- Lack of consent

14.8 There are inclusion or exclusion criteria based on gender, race or ethnicity:

Yes No

If **yes**, please explain the nature and rationale for the restrictions:

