11.0 Study Design

11.1 * Study design (Help Text updated 9/13):

We propose to test the efficacy of the Preventing Loss of Independence through Exercise (PLIÉ) program by performing a randomized, controlled trial (RCT) at adult day health centers that have current contracts with the San Francisco Veterans Affairs Medical Center (SFVA) or other local VA facilities. We propose to enroll participants in cohorts of 20 at a given center at a time and randomize them in blocks to Group 1 (n=10) or Group 2 (n=10) using a waitlist design. Veterans will be prioritized for enrollment. Study participants randomized to Group 1 will participate in the PLIÉ program at least 2 days/week, 1 hour/day for a 4-month intervention period while study participants randomized to Group 2 will engage in usual activities. After 4 months, Group 1 will 'graduate' and will be encouraged to engage in maintenance activities while Group 2 participates in PLIÉ at least 2 days/week, 1 hour/day for 4 months. Outcomes and potential mediators will be assessed in all study participants at baseline, 4 and 8 months to examine the effect of the intervention in both groups as well as maintenance of intervention effects post-intervention in Group 1. Study sites will include: Marin Adult Day Health Center in Novato, CA; Institute on Aging, San Francisco, CA; Catholic Charities, Santa Rosa, CA; and Alzheimer's Services of the East Bay, Oakland, CA. Other study sites will be added to the protocol over time.

11.2 If this is a clinical trial, check the applicable phase(s) (Help Text updated 9/13):

- Phase I
- Phase II
- Phase III
- Phase IV

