12.0 Scientific Considerations

12.1 Hypothesis (Help Text updated 9/13):

This study has a hypothesis:

Yes No

If yes, state the hypothesis or hypotheses:

1. Study participants will experience significantly greater improvements on the co-primary outcomes of cognitive function (Alzheimer's Disease Assessment Scale-cognitive subscale, ADAS-cog), physical performance (Short Physical Performance Battery, SPPB) and quality of life (Quality of Life in Alzheimer's Disease, QOL-AD) when participating in PLIÉ versus Usual Care (UC).
2. Caregivers will experience significantly greater reductions in caregiver burden (Caregiver Burden Inventory, CBI) and improvements in positive feelings about caregiving (Positive Aspects of Caregiving, PAC) when participating in PLIÉ versus UC.
3. The benefits of PLIÉ on participant and caregiver outcomes will be maintained from 4 to 8 months in Group 1.

12.2 * List the specific aims:

Aim 1. To determine whether PLIÉ improves participant outcomes over 4 months compared to Usual Care (UC).

Aim 2. To determine whether PLIÉ improves caregiver outcomes over 4 months compared to UC.

Aim 3. To determine whether the effects of PLIÉ are maintained over 4 months post-intervention.

12.3 Statistical analysis:

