All primary analyses will be performed using intent-to-treat principles. All variables will first be assessed for evidence of outlier values or skewed distributions. Baseline characteristics and potential confounders will be summarized for participants randomized to Group 1 versus Group 2 using standard methods such as means/standard deviations and medians/inter-quartile ranges for continuous variables and frequencies with percentages for categorical variables. Differences between the groups at baseline will be statistically tested using t-tests for continuous variables or non-parametric alternatives as indicated and Chi-square tests for categorical variables. Any differences detected will be adjusted for in multivariable models. Our primary analytic approach will be mixed effects linear regression which will enable efficient estimation of treatment effects, inclusion of all study participants in intent-to-treat analyses, and the same analytic approach to be used for all three Aims. Analyses will focus on differences in outcomes when participating in PLIE vs. UC. Fixed effects terms will be included for treatment (PLIE vs. UC), sequence (Group 1 vs. Group 2), time (baseline, 4 months, 8 months) and the interaction between treatment*time. Subjects will be modeled as random effects. Models also will adjust for any baseline differences in demographic factors or confounders that may occur due to chance. Covariates will be included to adjust for any co-interventions that occur (e.g., medication changes), and sensitivity analyses will be performed excluding participants who experience co-interventions. Standard diagnostic tests will be performed to examine model assumptions and distributions of residual values and to assess for potential leverage and influence points. To minimize the risk of Type I error due to multiple comparisons with co-primary outcomes, we will adjust p-values using bootstrapping (SAS Proc Multtest).

12.4 If this study has undergone scientific or scholarly review, please indicate which entity performed the review:

- Cancer Center Protocol Review Committee (PRC) (Full approval is required prior to final CHR approval for cancer-related protocols.)
- CTSI Clinical Research Center (CRC) advisory committee
- Departmental scientific review
- Other:

Specify **Other**:

Department of Veterans Affairs; SFVA R&D Committee

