Feasibility was assessed based on enrollment and retention. A total of 22 individuals were invited to participate in the study; of these, 8 declined (primarily due to lack of time/interest), 2 withdrew prior to the baseline assessment and 12 (55%) enrolled. Of the 12 who enrolled, 1 (PLIÉ) withdrew prior to the 18-week assessment (92% completion rate).

Effect sizes were estimated based on the mean standardized difference between PLIÉ and UC from baseline to 18 weeks (i.e., mean change from baseline to 18 weeks in PLIÉ group minus mean change from baseline to 18 weeks in UC group divided by the baseline standard deviation [SD] in both groups combined). We observed evidence of clinically meaningful between-group differences (≥ 0.25 SDs) for measures of cognitive function (ADAS-cog), physical performance (SPPB), quality of life (QOL-AD, participant and caregiver) and caregiver burden (CBI). **These effect sizes are substantially larger than has been observed with current dementia medications and affect a broader range of outcomes than current behavioral interventions.** These pilot data demonstrate convincingly that: 1) we can work successfully with community-based adult day health centers; 2) we can enroll and retain individuals with dementia and their caregivers in an integrative exercise intervention study; 3) we can successfully deliver the PLIÉ program to individuals with mild to moderate dementia; and 4) a larger study of the PLIÉ program is highly likely to find significant improvements in physical performance, cognitive function and quality of life and reduction in caregiver burden relative to usual care.

18-Week Change and Effect Size (ES) Calculations from PLIÉ Pilot Trial				
Measure	PLIÉ	UC	Baseline SD	Standardized ES†
Participant Measures				
Cognitive function (ADAS-cog)*	-4.6	2.4	9.2	+0.76
Physical performance (SPPB)	1.0	0.2	2.4	+0.34
Quality of life (QOL-AD)	6.0	2.6	4.1	+0.83
Caregiver Measures				
Participant quality of life (QOL-AD)	2.2	0.0	7.2	+0.33
Caregiver burden (CBI)*	-5.5	1.8	14.2	+0.49

* lower scores reflect better performance. † + values reflect better outcomes with PLIÉ; values ≥ 0.25 considered clinically meaningful.

13.3 References:

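### Section 14.4 states 81% power for SPPB and calls its planning design conservative, but the randomised 4-month comparison has about 68%

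*Combined protocol and SAP*

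**What the plan says.** Section 14.4 names mixed-effects regression on the waitlist design as the primary approach, but bases the sample size on something else: "based on the simpler (and more conservative) situation of a repeated measures design with 1 pre and 2 post measures". The inputs are the pilot effect sizes, a correlation of 0.75 and alpha 0.03. For SPPB (effect 0.34) the table gives 59 per group for 80% power, power 0.81 at 60 per group, and 0.71 with 20% attrition.

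Section 13.2 defines the pilot effect size from a single follow-up, as "mean change from baseline to 18 weeks in PLIÉ group minus mean change from baseline to 18 weeks in UC group", divided by the combined baseline SD.

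Section 11.1 describes the crossover: after 4 months "Group 1 will 'graduate' and will be encouraged to engage in maintenance activities while Group 2 participates in PLIÉ". It also says that the three visits serve "to examine the effect of the intervention in both groups as well as maintenance of intervention effects post-intervention in Group 1".

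In Section 12.2, Aim 1 compares PLIÉ with usual care over 4 months. Hypothesis 3 in Section 12.1 reads: "The benefits of PLIÉ on participant and caregiver outcomes will be maintained from 4 to 8 months in Group 1".

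Section 12.3 says: "Analyses will focus on differences in outcomes when participating in PLIE vs. UC". Besides treatment, its fixed effects are "sequence (Group 1 vs. Group 2), time (baseline, 4 months, 8 months) and the interaction between treatment*time", with subjects as random effects. It does not say which estimate is the primary test, or how Group 1 is coded at month 8 after it has finished PLIÉ.

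**The concern.** A design with one pre and two post measures gains precision by averaging two follow-ups, and needs an untreated control at both. Here Group 2 is on PLIÉ from month 4 to month 8, so usual care is a randomised comparator at the 4-month visit only. The second post measure cannot support the contrast for which it was counted.

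SPPB is the co-primary outcome that sets the sample size, and there is no slack: 59 per group needed, 60 planned. If true power for the 4-month comparison is well below 81%, a null SPPB result could be taken as coming from an adequately powered test when it did not. The label matters as well as the number, because readers are told that the approximation errs on the safe side.

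**Working it through.** **Inputs.** SPPB effect 0.34 baseline SD, correlation rho = 0.75, alpha 0.03, target power 80%, 60 per group, or 48 after 20% attrition (Sections 13.2 and 14.4). Sidedness is not stated. Two-sided is inferred, because one-sided 0.03 would give power 0.88 and 0.80, which does not match the table. Compound symmetry is assumed, in line with a single correlation and a random subject effect.

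**Formulas.** With a variance factor f in units of the baseline variance:
- n per group = 2 (z[0.985] + z[0.80])² f / ES², where (2.170 + 0.842)² = 9.07
- power = Phi( ES / sqrt(2f/n) − 2.170 )

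**Step 1: reproduce the plan's figures.** For a change score with 1 pre and 2 post measures, f = (1 + rho)/2 + 1 − 2rho = 0.875 + 1 − 1.5 = 0.375.
- n = 2 × 9.07 × 0.375 / 0.1156 = 58.85, so 59.
- Power at 60: 0.34 / sqrt(0.75/60) = 3.041; Phi(0.871) = 0.808.
- Power at 48: 0.34 / sqrt(0.75/48) = 2.720; Phi(0.550) = 0.709.

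These are the printed 59, 0.81 and 0.71. The same f gives the printed n for ADAS-cog (12), QOL-AD (10) and CBI (29). The printed CBI power (0.97 and 0.92) does not follow from it (0.987 and 0.960), so CBI is not used as evidence.

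**Step 2: the 4-month contrast.**
- Change score, 1 pre and 1 post: f = 2(1 − rho) = 0.50. n = 78.46, so 79. Power at 60: 0.34 / sqrt(1/60) = 2.634; Phi(0.463) = 0.679. Power at 48: Phi(0.185) = 0.574.
- Section 12.3 model, with Group 1 coded off PLIÉ at month 8 (on/off coding): sequence, three-level time, treatment and treatment*time use six parameters for six group-by-visit means. The model is saturated, month-8 data add nothing to the 4-month effect, and f is again 0.50.
- Baseline-adjusted, no sequence term: f = 1 − rho² = 0.4375. n = 68.66, so 69. Power is 0.741 at 60 and 0.636 at 48.

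| SPPB analysis | f | n for 80% | Power, 60 | Power, 48 | Detectable effect at 80% power, 60 (48) |
|---|---|---|---|---|---|
| Stated: parallel, 1 pre/2 post | 0.375 | 59 | 81% | 71% | 0.34 (0.38) |
| 4-month: change score or 12.3 model, on/off | 0.50 | 79 | 68% | 57% | 0.39 (0.43) |
| 4-month: baseline-adjusted, no sequence | 0.4375 | 69 | 74% | 64% | 0.36 (0.41) |

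To reach 81% at month 4, rho would have to be about 0.81 (change score) or 0.79 (baseline-adjusted).

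**Step 3: the pooled three-visit effect.** Let d be the 4-month effect and r the share of it that Group 1 retains at month 8. The true means are then (0, d, rd) in Group 1 and (0, 0, d) in Group 2.

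With on/off coding, f = 0.125 and the expected estimate is d(2 − r)/2:

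| Benefit retained, r | Power, 60 | Power, 48 |
|---|---|---|
| 0% | 99.9% | 99.4% |
| 50% | 96% | 91% |
| 75% | 87% | 78% |
| 84.5% | 81% | 71% |
| 90% | 77% | 66% |
| 100% | 68% | 57% |

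At r = 100% the estimate is biased to d/2: (0.34/2) / sqrt(0.25/60) = 2.634, the same ratio as in Step 2.

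With month 8 coded as PLIÉ in Group 1, f = 0.375 with the sequence term and 0.357 without. At full retention, power is 81% (71%) and 83% (73%). At lower retention power rises, but the estimate is inflated: with the sequence term its expectation is d(1 + (1 − r)/2), or 1.25d at r = 50%. Under this coding everyone is on PLIÉ at month 8, so the month-8 treatment*time column duplicates the month-8 time column. The design matrix has rank 5 of 6, and the listed interaction cannot be estimated.

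**Step 4: the other co-primaries.** With f = 0.50, ADAS-cog and QOL-AD keep 99.9% power or more, even at 48 per group.

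**The case against.** The strongest reply is that Section 14.4 compares its planning design with the whole waitlist mixed model, not with the 4-month contrast. The Section 12.3 focus on periods in and out of PLIÉ, and the Section 11.1 interest in both groups, support a pooled reading. Aim 1's 4 months could mean the length of exposure in either group. On that reading, with on/off coding, the planning figure is conservative as long as Group 1 retains less than about 85% of the benefit.

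This stands as a possible reading, but it does not support an unqualified claim. Hypothesis 3 expects the benefit to be maintained, and at full retention the pooled on/off test has the same 68%, with a halved estimate. The alternative coding with the sequence term only equals the stated power at full retention, and it makes a listed model term inestimable.

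Three further points limit the finding:
- The 57% puts all 20% attrition before month 4. That is the plan's own convention, since 48 per group reproduces its 0.71. If only half were lost by then (an assumption), 54 per group gives 63%. Keeping dropouts' baselines in the mixed model gives 58.5%.
- The effect size is in baseline SD units, so it can be used with two post measures if a constant effect is assumed. That it comes from one follow-up is not a separate defect.
- The pilot estimate is imprecise. With 6 and 5 completers and rho 0.75, its standard error is about sqrt(0.5 × (1/6 + 1/5)) = 0.43 SD, larger than 0.34 itself.

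**Conclusion.** The concern holds. There is no arithmetic error in the SPPB row; the design behind it is not this trial's design. For the randomised 4-month comparison, power is 13 points lower than stated at full enrolment (68% against 81%) and 14 points lower with attrition (57% against 71%). Baseline adjustment without the sequence term recovers about half of the gap. For the pooled effect, the claim to be conservative cannot be confirmed from the documents, because neither the month-8 coding nor the carry-over is stated.

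The figures rest on two-sided alpha 0.03, rho 0.75 at all visits, the pilot effect of 0.34, and on/off coding where the Section 12.3 model is used. That is the only one of the two codings under which all its listed terms can be fitted. The consequence is confined to SPPB among the co-primaries. It concerns an accurate statement of planned power and is not a case for a larger trial. It should be fixed.

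**What to change.** In Section 14.4, give SPPB power for the 4-month contrast: 68% (57% with 20% attrition, counted as 48 per group at month 4) under the Section 12.3 model. If Section 12.3 is changed to a baseline-adjusted analysis without the sequence term, give 74% (64%) instead. Remove the unqualified statement that the planning design is the more conservative one, and state that alpha is two-sided.

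If the pooled three-visit effect is to be the primary test, say so in Section 12.3. State there how Group 1's month-8 visit is coded and what carry-over is assumed, and in Section 14.4 give power under that coding, including the full maintenance that Hypothesis 3 expects.

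The cost is a rewording of Section 14.4, a short addition to Section 12.3 if either alternative is chosen, and a less favourable stated power for SPPB if the 4-month contrast is reported. Enrolment does not change.

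### Does planning at an underived alpha of 0.03 make the SPPB power in section 14.4 wrong for the bootstrap adjustment in section 12.3?

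*Combined protocol and SAP*

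**What the plan says.** Section 12.1 names three co-primary outcomes: ADAS-cog, SPPB and QOL-AD. For multiplicity, section 12.3 says "we will adjust p-values using bootstrapping (SAS Proc Multtest"). It states no familywise level and no form of the bootstrap. The model has fixed effects for treatment, sequence, "time (baseline, 4 months, 8 months) and the interaction between treatment*time".

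Section 14.4 bases power on the "simpler (and more conservative) situation of a repeated measures design with 1 pre and 2 post measures", with correlation 0.75 between measures and an "estimated alpha=0.03 (to account for multiple comparisons for our three co-primary outcomes"). For SPPB (effect size 0.34) its table gives 59 per group for 80% power, power 0.81 at 60 per group, and 0.71 with 20% attrition. ADAS-cog (0.76) and QOL-AD (0.83) have power 1.00 throughout. The text summarises: "Power ranged from 71% to 100% for all outcomes even with 20% attrition". No correlation between the three outcomes is given.

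Section 11.1 adds that after 4 months Group 1 "will be encouraged to engage in maintenance activities while Group 2 participates in" the programme.

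**The concern.** The level used for planning is not tied to the test that will be run. A value of 0.03 is neither 0.05 nor 0.05/3 = 0.017, and the documents do not say where it comes from. If each outcome really were tested at 0.03, the familywise error would be 8.7% with uncorrelated outcomes and 6.8% at correlation 0.7. So 0.03 cannot be read as an allocation of 5% at those correlations.

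SPPB is the outcome for which this matters. At 60 per group its stated power is only just above 80%, so a stricter effective level would take it below. The unstated choice between single-step and step-down would then decide whether the trial is described as adequately powered for physical performance.

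**Working it through.** **Inputs from section 14.4:** effect sizes 0.76, 0.34 and 0.83; correlation 0.75; one pre and two post measures; alpha 0.03; 60 per group, or 48 after 20% attrition. **Assumed, not in the documents:** a two-sided 5% familywise level, and a common correlation r between the three test statistics.

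**1. The plan's own figures.** For the mean of two post measures minus the pre measure, the variance factor is V = (1 + 0.75)/2 + 1 - 2 × 0.75 = 0.375. Power = Φ(0.34/√(2V/n) - z).

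- n = 60: 0.34/√(0.75/60) = 3.041. With z = 2.170 (two-sided 0.03), power = Φ(0.871) = 0.808.
- n = 48: 0.34/√(0.75/48) = 2.720, so power = Φ(0.550) = 0.709.
- 80% power: n = 0.75 × (2.170 + 0.842)²/0.34² = 58.8, so 59.

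All three match the table, as do 12 for ADAS-cog and 10 for QOL-AD. A one-sided 0.03 does not match (49 per group). The power entries for the secondary outcome CBI do not reproduce this way (0.99 and 0.96 against 0.97 and 0.92), but nothing here depends on that row.

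**2. Single-step at familywise 5%.** The critical value c is that of the largest of three equally correlated |z| statistics.

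| r | c | level per test | power, n = 60 | power, n = 48 | n for 80% |
|---|---|---|---|---|---|
| 0 | 2.388 | 0.0170 | 0.743 | 0.630 | 68 |
| 0.5 | 2.349 | 0.0188 | 0.756 | 0.645 | 66 |
| 0.7 | 2.298 | 0.0216 | 0.771 | 0.664 | 64 |
| 0.8 | 2.254 | 0.0242 | 0.784 | 0.679 | 63 |
| 0.9 | 2.185 | 0.0289 | 0.804 | 0.704 | 60 |

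A level of 0.03 per test would need r of about 0.92.

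**3. Step-down at familywise 5%.** At the plan's effects, ADAS-cog and QOL-AD each have power above 0.9999 even at 0.05/3. They are rejected almost surely, which leaves SPPB tested at 0.05: Φ(3.041 - 1.960) = 0.860 at n = 60, and Φ(2.720 - 1.960) = 0.776 at n = 48. Simulation of correlated z-statistics (not of the bootstrap itself) for r from 0 to 0.7 gives the same values, and these for other effects:

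| effects of the other two outcomes | SPPB power, n = 60 | n = 48 |
|---|---|---|
| as in the plan | 86% | 78% |
| half of the pilot values | 84-85% | 74-75% |
| both 0.34 | 82-83% | 71-72% |
| ADAS-cog 0.76, QOL-AD 0.2 | 81% | 71% |
| ADAS-cog 0.76, QOL-AD null | 79-81% | 69-71% |
| both null | 74-77% | 63-66% |

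**4. Where 0.81 falls.** Against the stated 0.81, single-step is 0.81 - 0.743 = 6.7 to 0.81 - 0.771 = 3.9 points lower for r from 0 to 0.7. Step-down at the plan's effects is 0.86 - 0.81 = 5 points higher. The stated value is inside the bracket.

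**5. Does the 8-month visit undermine the formula?** By 8 months Group 2 has received PLIÉ, so the second post measure is not a parallel comparison. Take contrasts of the between-group differences at 0, 4 and 8 months, with weights summing to zero. The variance factor is then (1 - 0.75) × (sum of squared weights).

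- Plan's formula, weights (-1, ½, ½): 0.25 × 1.5 = 0.375.
- Single treatment term, Group 1 coded as still treated at 8 months, weights (-½, 1, -½): 0.25 × 1.5 = 0.375.
- Single treatment term, Group 1 coded as usual care at 8 months, weights (0, ½, -½): 0.25 × 0.5 = 0.125.
- Treatment*time contrast at 4 months, weights (-1, 1, 0): 0.25 × 2 = 0.5.

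Only the last is less precise than the plan assumed; it would give 75% and 65% when SPPB is tested at 0.05. With a single treatment term, the plan's formula is matched or improved on.

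**The case for a change.** The strongest case for a change is that the bracket straddles 80%. Single-step at correlations up to 0.7 needs 64 to 68 per group, more than the 60 planned, whereas step-down has power to spare. A plan that leaves this open also leaves the analyst a choice that could decide whether SPPB is declared significant.

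The first part stands as arithmetic, but it depends on a familywise level and outcome correlations that the documents do not give. The upper end of the bracket depends on pilot effects from 12 people (7 and 5 per arm). Given that uncertainty, a level between the two forms is a fair planning allowance, and section 14.4 itself calls it an estimate. Nor do the documents say that SPPB alone fixed the number: six sites of 20 also give 120.

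The second part carries less weight than it seems. Step-down rejects everything that single-step rejects at the same level, and possibly more, and it controls the familywise error. Choosing the more favourable of the two, even late, therefore yields no more than step-down and cannot inflate the error.

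Which model term supplies the p-value is a real open question, but it concerns the effect being estimated and is separate from the 0.03.

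**Conclusion.** The omissions are real: 0.03 is not derived, and section 12.3 names neither the familywise level nor the bootstrap form. They do not make the plan wrong. The SPPB figures of 59, 0.81 and 0.71 are correct at the level stated. Type I error is governed by the adjusted p-values, not by the planning alpha.

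At an assumed 5% familywise level, with the plan's 0.34 and its variance formula, SPPB power at 60 per group runs from about 74% (single-step, uncorrelated outcomes) to about 86% (step-down at the plan's effects). The stated 81% sits between them, so it cannot be called too high or too low. Filling the gap with either form is ordinary analytic practice; step-down would be one good choice, but it is not a correction of a method the plan states. Enrolment is unaffected. No change follows.
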